6.1.5 Visit 6 (Day 30)

- Obtain vital sign measurements (BP, HR, body temperature, and O₂ saturation.)
- Conduct symptom-directed physical exam, as needed
- Record any concomitant medications.
- Record any adverse events.
- Collect PK blood sample at 24-hours post dose
- Collect PK blood sample at 30-hours post dose

6.1.6 Visit 7 (Day 31)

- Obtain vital sign measurements (BP, HR, body temperature, and O₂ saturation.)
- Conduct symptom-directed physical exam, as needed
- Record any concomitant medications.
- Record any adverse events.
- Collect blood samples for CANs, CD62L, iFABP and LPS at 48-hours post dose.
- Collect blood samples for hematology and blood chemistry
- Collect urine sample for 3-indoxyl sulfate.
- Collect PK blood sample at 48-hours post dose

6.1.7 Visit 8 (Day 32)

- Obtain vital sign measurements (BP, HR, body temperature, and O₂ saturation.)
- Conduct symptom-directed physical exam, as needed
- Record any concomitant medications.
- Record any adverse events.
- Collect PK blood sample at 72-hours post dose

6.1.8 Visit 9 (Day 43 ± 3 days) EOS Visit

The following assessments are to be completed at the EOS Visit:

- Collect any adverse events since Visit 8.
- Collect concomitant medication changes since Visit 8. Specifically collect opioid use since Visit 8.
- Obtain subject's weight.
- Obtain vital sign measurements (BP, HR, body temperature, and O₂ saturation.)
- Conduct symptom-directed physical exam, as needed.
- Obtain ECG (12-lead) if abnormal findings were observed at Visit 5 (Day 29).
- Conduct urine pregnancy test for WOCBP.

- Collect blood samples for hematology and blood chemistry and urine for urinalysis only if needed for follow-up of AEs or SAEs.
- Collect blood samples for CANs, CD62L, iFABP and LPS.
- Collect urine sample for 3-indoxyl sulfate
- Query subject and record VOCs that have occurred since Visit 5.
- Record any concomitant medications.
- Record any adverse events.
- Discharge subject from study. Follow subject for AEs or SAEs as described in Section 7.7.

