	
Blood samples for PK analysis will be collected at the following timepoints:
 
• Day 1: pre-dose, 0.5, 1, 1.5, 2, 3, 4, 5, and 8-hours post-dose• Day 8 and Day 15: pre-dose and 0.5, 1, and 2-hours post-dose.• Day 29: pre-dose, 0.5, 1, 1.5, 2, 3, 4, 5, and 8-hours post-final dose.• Day 30: 24 and 30 hours post-final dose• Day 31: 48 hours post-final dose• Day 32: 72 hours post-final dose• During medical facility visit for VOC with estimated time of last dose, when possible. 
PD biomarkers (absolute neutrophil count [ANC], circulating aged neutrophils [CANs], serum CD62L, high sensitivity C-reactive protein [hsCRP], the gut permeability biomarkers intestinal fatty-acid binding protein [iFABP], lipopolysaccharide [LPS], and the gut bacteria biomarker urine 3-indoxyl sulfate [3-IS Urine]) will be collected at the following timepoints:
 
• Day 1: pre-dose• Day 8, Day 15, and Day 29: during each visit – pre dose• Day 31• Day 43• During medical facility visit for VOC, when possible. 
Safety:
 
Safety will be assessed throughout the duration of the study by collection of adverse events (AEs), vital signs (systolic and diastolic blood pressure, heart rate, oral body temperature, and oxygen saturation), clinical safety laboratory tests (hematology, chemistry, urinalysis, and C-reactive protein), physical exams (PEs), and electrocardiograms (ECGs).
 
Exploratory Assessments:
 
At every study visit, subjects will report, and the site staff will record, opioid use since their previous visit.
 
Information on any potential VOCs experienced during the study will be collected as follows:

--	---

	
 • Dates and duration of each episode. A VOC is defined as: 
 ○ The occurrence of appropriate symptoms consistent with a painful crisis, acute chest syndrome (ACS), or priapism, and ○ Requires visit to a medical facility, and ○ Receipt of either a parenteral or oral opioid or NSAID analgesia. • Categorization of VOCs. Subcategories are uncomplicated pain crises, acute chest syndrome (ACS), hepatic sequestration, splenic sequestration, and priapism (requiring healthcare visit). • Intravenous opioid analgesia (IOA) and oral opioid use during VOCs, including date/time of each start and stop of treatment, dose, drug, inpatient/outpatient setting, and date/time of readiness-to-discharge.

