2.2 Endpoints

2.2.1 Pharmacokinetics and Pharmacodynamics

Full rifaximin and 25-desacetyl rifaximin plasma PK profiles following administration on Days 1 and 29 and C_{max} and C_{trough} on Days 8, 15, and 29 will be evaluated.

Blood samples for PK analysis will be collected at the following timepoints:

- Day 1 and Day 29: pre-dose, 0.5, 1, 1.5, 2, 3, 4, 5, and 8-hours post-dose.
- Day 8 and Day 15: pre-dose and 0.5, 1, and 2-hours post-dose.
- Day 29: pre-dose, 0.5, 1, 1.5, 2, 3, 4, 5, and 8-hours post-final dose
- Day 30: 24 and 30 hours post-final dose
- Day 31: 48 hours post-final dose
- Day 32: 72 hours post-final dose
- During medical facility visit for VOC with estimated time of last dose, when possible.

PD biomarkers (ANC, CANs, serum CD62L, hsCRP, the gut permeability biomarkers serum iFABP and LPS, and the gut bacteria biomarker urine 3-indoxyl sulfate) will be collected at the following timepoints:

- Day 1: pre-dose
- Day 8, Day 15, and Day 29: during each visit – pre dose
- Day 31
- Day 43
- During medical facility visit for VOC, when possible.

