6.2.2 Assessments of Pharmacodynamics

The pharmacodynamics of rifaximin ER and DER will be assessed through collection of ANC, CANs, serum CD62L, hsCRP, the gut permeability biomarkers serum iFABP and LPS, and the gut bacteria biomarkers urine 3-indoxyl sulfate according to the schedule in [Appendix 1](#). These assessments will be conducted at a central laboratory. Instructions for collection, preparation, storage, and shipment of samples will be provided in the Laboratory Manual.

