
Hematology
 
 • Hemoglobin • Hematocrit • White blood count and differential • Red blood cell count • Percent and absolute reticulocyte count • Platelet count 
Coagulation
 
 • Prothrombin time • INR 	
Serum Chemistry
 
 • Blood Urea Nitrogen • Bilirubin (total, direct, and indirect) • Alkaline phosphatase • Aspartate aminotransferase • Alanine aminotransferase • Albumin • Sodium • Potassium • Magnesium • Calcium • Chloride • Bicarbonate • Glucose • Creatine kinase • Creatinine • Lactate dehydrogenase • High sensitivity C-Reactive protein (hs-CRP) • Total globulin • Total protein • Lipid Panel 
 - Total cholesterol - HDL - LDL - Triglycerides

Additional Tests
 
 • Hemoglobin genotype (if not previously determined) using HPLC/electrophoresis • Serum pregnancy test (WOCBP only)* • Urine pregnancy test (WOCBP only) 
* WOCBP, women of child-bearing potential
	

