- b. Medical history will be obtained from prior 3 months. Detailed history of VOCs occurring over the past 12 months will be obtained. This will include collection of treatments for VOCs including drug, dose, route of admin, duration of treatment, and inpatient/outpatient setting.
- c. Vital signs will be obtained after the subject has been in a supine position for a minimum of 5 minutes. Vital signs include systolic and diastolic blood pressure, heart rate, body temperature, and oxygen saturation.
- d. Perform a full physical examination at Screening and symptom-directed physical examination at subsequent visits.
- e. A 12-lead ECG (supine) will be performed. An ECG will be performed at the Day 43 (EOS) Visit only if abnormal findings were observed at the Day 29 (EOT/ET) Visit.
- f. Hemoglobin genotyping will be recorded if known. If unknown at Screening, hemoglobin genotyping will be performed using HPLC/electrophoresis.
- g. Serum pregnancy test is to be performed at Screening for all women of childbearing potential. A negative Screening serum pregnancy test and a negative urine pregnancy test must be confirmed before randomization. Subsequent pregnancy testing will be with urine pregnancy test.
- h. Information on whether a VOC requiring a visit to a medical facility occurred will be recorded. Medications received during the VOC visit will be recorded.
- i. Only weight will be collected.
- j. Hematology, chemistry, and/or urinalysis will only be collected at this visit if needed for follow-up or resolution of AEs/SAEs.
- k. Not all treatment groups will return study drug at Visit 3 and Visit 4.
- l. During Screening, record all opioid use for the prior 30 days. At each visit, record all opioid use since the previous visit.

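### ANC and hsCRP are listed as Day 43 PD markers, but the visit schedule draws their only stated source panels that day solely for adverse-event follow-up

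*Combined protocol and SAP*

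**What the plan says.** Two places define which PD markers are collected and when.

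- Synopsis, Criteria for Evaluation: "PD biomarkers (absolute neutrophil count [ANC], circulating aged neutrophils [CANs], serum CD62L, high sensitivity C-reactive protein [hsCRP", followed by the remaining markers and a list of time points that includes Day 43.
- Section 2.2.1: "PD biomarkers (ANC, CANs, serum CD62L, hsCRP, the gut permeability biomarkers serum iFABP and LPS", plus urine 3-indoxyl sulfate, with the same time points.

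In both lists Day 43 stands without a qualifier. The VOC visit in the same lists is qualified as applying where feasible.

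Section 6.2.2 states "The pharmacodynamics of rifaximin ER and DER will be assessed through collection of ANC, CANs, serum CD62L, hsCRP" and the other markers, and refers to Appendix 1 for the schedule.

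Table 2 in Section 6.2.3.1 shows where the two markers come from. Hematology contains "White blood count and differential", and Serum Chemistry contains "High sensitivity C-Reactive protein (hs-CRP".

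Two places govern those panels at Day 43.

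- Section 6.1.8: "Collect blood samples for hematology and blood chemistry and urine for urinalysis only if needed for follow-up of AEs or SAEs".
- Appendix 1, footnote j, on the Day 43 cell of the Hematology and Chemistry row: "Hematology, chemistry, and/or urinalysis will only be collected at this visit if needed for follow-up or resolution of AEs/SAEs".

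For analysis, the synopsis plans summaries by treatment of level and change from Baseline. For ANC this applies at the visits where it is collected; for hsCRP it applies at every visit. Section 8.0 lists the SD among the planned statistics. Section 8.4.13 uses available data only and imputes nothing.

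**The concern.** The endpoint text requires ANC and hsCRP from every subject at Day 43. The operational text obtains them only when an adverse event calls for laboratory follow-up. Both cannot hold.

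If the operational text prevails, the Day 43 rows for these markers come from a subset selected on clinical course. Neutrophil count and CRP may well be related to having such an event, so the subset could be unrepresentative as well as small. The direction of any bias cannot be predicted. A vaso-occlusive crisis alone would not trigger the draw, because Sections 6.1.9 and 7.3 keep those events out of adverse-event reporting.

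PD characterisation is part of the first study objective, and Day 43 is the only scheduled PD point two weeks after the last dose. Within one by-visit table, ANC and hsCRP would describe different subjects from the other five markers. If some sites followed one text and some the other, the mix would also depend on site.

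**Working it through.** **Setting the texts side by side for Day 43**

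| Marker | Listed as PD at Day 43 (synopsis, 2.2.1) | Row in Appendix 1 | Drawn at Day 43 under 6.1.8 |
|---|---|---|---|
| CANs, serum CD62L, iFABP, LPS | Yes | Yes | Everyone |
| Urine 3-indoxyl sulfate | Yes | Yes | Everyone |
| ANC (from the differential) | Yes | None | Adverse-event follow-up only |
| hsCRP (from chemistry) | Yes | None | Adverse-event follow-up only |

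**Is Day 43 the only affected visit?** Yes. Sections 6.1.2, 6.1.3 and 6.1.4 draw hematology and chemistry unconditionally on Days 1, 8, 15 and 29. For Day 31, Section 6.1.6 states "Collect blood samples for hematology and blood chemistry" with no condition.

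**Does another passage supply the missing values?** None does. Section 6.2.2 defers to Appendix 1, which has no row for either marker, although its abbreviation key still defines hsCRP. Section 2.2.2 names hsCRP apart from chemistry in its list of safety tests, but no visit has a separate hsCRP draw.

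**How thin could the Day 43 data be?** The plan gives no figure to reproduce, and Section 8.2 says the sample size has no formal basis. The share *p* of subjects needing laboratory follow-up at Day 43 is therefore an assumption, shown over a range.

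Inputs: 12 subjects per active arm and combined placebo of 6 + 6 = 12 (Sections 3.2 and 8.4.1). The total is 4 × 12 + 2 × 6 = 60. Dropout is ignored.

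Let X be the number of values in one 12-subject column, X ~ Binomial(12, *p*). Then

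- mean per column = 12*p*; mean over the study = 60*p*;
- P(X ≤ 1) = (1 − *p*)^12 + 12*p*(1 − *p*)^11, the chance that no SD can be calculated.

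| Assumed *p* | Mean per column | Mean of 60 | P(X ≤ 1) |
|---|---|---|---|
| 0.10 | 1.2 | 6 | 0.659 |
| 0.20 | 2.4 | 12 | 0.275 |
| 0.30 | 3.6 | 18 | 0.085 |
| 0.50 | 6.0 | 30 | 0.003 |

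With unconditional collection the planned number is 12 per column and 60 overall, before dropout.

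**The case against.** The strongest reply is that this is a drafting slip with little consequence. Section 6.1.8 and Appendix 1 agree with each other, and the outlier is a time-point list shared by all PD markers. The PD summaries are descriptive. The optional exposure-response analyses, and the dose-response analyses for PD endpoints other than CANs, are tied to Day 29, and no named analysis depends on Day 43 ANC or hsCRP. This stands, and it limits the seriousness of the point. It also suggests most sites would follow the schedule, which is the reading that loses the data.

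Second, the ANC summary is confined to visits where ANC is collected, so a gap is tolerated. This helps only in part. Section 2.2.1 says ANC is collected at Day 43, and the clause would still allow a Day 43 ANC summary built on the selected subset. The hsCRP sentence has no such limit.

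Third, the values might be obtained another way. Table 2 names the differential rather than ANC, so that source is inferred. A total neutrophil count might be recovered from the CAN count and percentage, hsCRP might be run on the serum drawn for other markers, and the Laboratory Manual might say so. Section 6.2.3.1 also lets the investigator take extra blood. The documents state none of these as the Day 43 plan, and discretionary blood is not scheduled collection. The CAN argument can also cut the other way: if the CAN count is calculated from the differential, Day 43 CAN counts would be affected too. The documents do not say how it is obtained.

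Finally, the binomial figures rest on an assumed rate and span most outcomes. That is correct. They show what thin data would mean and are not evidence for the contradiction.

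**Conclusion.** The concern holds. The contradiction follows from the text without any assumption, and is firmest for hsCRP, which Table 2 names explicitly; for ANC it rests on the differential being the source. It affects two of seven PD markers at one off-treatment visit. If the visit schedule is followed, Day 43 values for these markers will come from a non-representative subset of unknown size. The illustrative range is 1.2 to 6 values per 12-subject column for an assumed share of 10% to 50%. It should be corrected, but it does not threaten the Day 29 PD results or the PK objective.

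**What to change.** Reconcile the passages in one of two ways.

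1. **Collect from everyone.** In Section 6.1.8 and Appendix 1, make the blood count with differential and hsCRP unconditional PD samples at Day 43. Add ANC and hsCRP rows to Appendix 1, and leave the remaining safety laboratory tests conditional. The cost is two routine tests for up to 60 subjects at a visit where blood is already taken for CANs, CD62L, iFABP and LPS, so no extra venepuncture is needed.
2. **Drop the time point.** Remove Day 43 for ANC and hsCRP from the synopsis and Section 2.2.1, and from their by-visit summaries. This is a text edit only, but it gives up the two-week off-treatment value for both markers.

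The first option keeps all seven markers on the same subjects. Under either option, Day 43 CANs stay as planned; the sponsor should confirm from the Laboratory Manual that the CAN count does not depend on the conditional differential.

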6.1.9 Visit to a Medical Facility for a VOC Event

The following assessments are to be completed, when possible, when a subject visits a medical facility for treatment of a VOC:

- Collect any adverse events since previous visit. Do not record VOC events as an AE (See [Section 7.3](#)).
- Collect concomitant medication changes since previous visit. Specifically collect opioid use.
- Obtain vital sign measurements (BP, HR, body temperature, and O₂ saturation).
- Conduct symptom-directed physical exam.
- Collect blood samples for hematology and blood chemistry and urine for urinalysis.
- Collect blood samples for CANs, CD62L, iFABP and LPS.
- Collect PK blood samples.
- Collect urine sample for 3-indoxyl sulfate.

6.1.10 Unscheduled Visit

The Investigator may perform an unscheduled visit at any time during the study at his/her discretion. Assessments performed at an unscheduled visit should be symptom directed.

The following procedures must be performed at all unscheduled visits:

- Collect and record hospital admission and death data.
- Safety laboratory testing. Repeat laboratory testing may be needed based on results from the unscheduled laboratory testing.

- Concomitant medications
- Adverse events

If the subject is discontinued from the study at an unscheduled visit, the visit will be considered Visit 9 (EOT) and all of the EOT assessments should be completed.

6.2 Outcome Assessments

Endpoints are presented in [Section 2.2](#). Analyses are described in [Section 8.0](#).

The following assessments will be utilized throughout the study.

6.2.1 Assessment of Pharmacokinetics

Blood samples for analysis of plasma rifaximin and 25-desacetyl rifaximin pharmacokinetics will be collected as described in [Appendix 2](#). Full PK assessments through 8-hour and 72-hours post dose will be performed at Visit 2 (Day 1) and Visits 5 to 8 (Days 29 to 32), respectively. Samples will be obtained pre-dose and at 0.5, 1, 1.5, 2, 3, 4, 5, and 8-hours post-dose on Days 1 and 29.

At Visit 3 (Day 8) and Visit 4 (Day 15) samples will be obtained pre-dose and at 0.5, 1, and 2-hours post-dose.

Additionally, post-final dose assessments will be done on:

Visit 6: 24 and 30 hours post-final dose

Visit 7: 48 hours post-final dose

Visit 8: 72 hours post-final dose.

The windows around the collection timepoints are:

- within 15 minutes prior to dose for pre-dose samples,
- ± 5 minutes for samples taken at 0.5 hours through 1.5 hours, and
- ± 10 minutes for samples taken 2 hours through 8 hours.
- ± 2 hours for samples taken 24 hours through 72 hours.

In addition, when possible, a sample will be obtained for PK assessment during a medical facility visit for a VOC. The time of the last dose of study drug will be recorded.

If the subject is to begin treatment with a P-gp inhibitor, a plasma sample for PK analysis should be collected during treatment with both rifaximin and the P-gp inhibitor. This sample should be collected at the next scheduled visit, if possible. Alternately, an unscheduled PK sampling visit

should occur. The date and time of the last 2 rifaximin doses, as well as the last 2 doses of the P-gp inhibitor should be recorded.

Study participants should be instructed to take the study drug on an empty stomach. The morning (AM) dose should be taken on an empty stomach, and subjects must avoid food for two hours after taking the study drug. The evening (PM) dose should be taken on an empty stomach (at least two hours after the last meal), and subjects must avoid food for two hours after taking the study drug.

On Days 1, 8, 15, and 29, Participants will fast for a minimum of 10 hours prior to, and 2 hours after, the morning study drug administration. Water will be restricted from one hour prior to dosing through one hour following dosing, except for the water that will be consumed at dosing.

6.2.2 Assessments of Pharmacodynamics

The pharmacodynamics of rifaximin ER and DER will be assessed through collection of ANC, CANs, serum CD62L, hsCRP, the gut permeability biomarkers serum iFABP and LPS, and the gut bacteria biomarkers urine 3-indoxyl sulfate according to the schedule in [Appendix 1](#). These assessments will be conducted at a central laboratory. Instructions for collection, preparation, storage, and shipment of samples will be provided in the Laboratory Manual.

6.2.3 Assessment of Safety

Safety endpoints are presented in [Section 2.2.2](#). Safety will be assessed throughout the duration of the study.

Safety assessments will include the following:

- Adverse events (AEs),
- Vital signs (systolic and diastolic blood pressure, heart rate, oral body temperature, and oxygen saturation),
- Clinical safety laboratory tests,
- Physical exams (PES), and
- Electrocardiograms (ECGs).

6.2.3.1 Clinical Laboratory Tests

Clinical laboratory tests to be performed during the study are outlined in Table 2. The samples will be analyzed by a central clinical laboratory. Exceptions may be made as necessary for local laboratory testing. At the Investigator's discretion, additional blood may be collected for clinical laboratory tests. Results from laboratory specimens collected during Screening must be received by the site prior to Visit 2.

Note: CANs assay examiners will be trained and certified on CANs assessment requirements using flow cytometry prior to screening patients (conducted on separate, healthy volunteers).

It is the responsibility of the Investigator to assess the clinical significance of all abnormal clinical laboratory values as defined by the list of normal values on file for the central laboratory. All clinically significant laboratory value abnormalities are to be recorded as AEs.

A clinically significant laboratory value is any abnormal result that, in the judgment of the Investigator, is an unexpected or unexplained laboratory value or if medical intervention or corrective action (transfusion, hydration, initiation of antibiotics or other concomitant medication) is required. Any abnormal values that persist should be followed at the discretion of the Investigator. Additional and repeat laboratory safety testing for the evaluation of abnormal results and/or AEs during the study may be performed at the discretion of the Investigator or upon request of the Sponsor. Repeat laboratory testing of abnormal potentially clinically significant or clinically significant results for the Screening evaluation of the subject may be repeated once at the discretion of the Investigator.

Tests listed in [Table 2](#) will be performed as outlined in the Schedule of Assessments ([Appendix 1](#)). Details on collection, preparation, and shipping of blood samples are provided in the Laboratory Manual.

Table 2. Clinical Laboratory Tests


Hematology
 
 • Hemoglobin • Hematocrit • White blood count and differential • Red blood cell count • Percent and absolute reticulocyte count • Platelet count 
Coagulation
 
 • Prothrombin time • INR 	
Serum Chemistry
 
 • Blood Urea Nitrogen • Bilirubin (total, direct, and indirect) • Alkaline phosphatase • Aspartate aminotransferase • Alanine aminotransferase • Albumin • Sodium • Potassium • Magnesium • Calcium • Chloride • Bicarbonate • Glucose • Creatine kinase • Creatinine • Lactate dehydrogenase • High sensitivity C-Reactive protein (hs-CRP) • Total globulin • Total protein • Lipid Panel 
 - Total cholesterol - HDL - LDL - Triglycerides

Additional Tests
 
 • Hemoglobin genotype (if not previously determined) using HPLC/electrophoresis • Serum pregnancy test (WOCBP only)* • Urine pregnancy test (WOCBP only) 
* WOCBP, women of child-bearing potential
	

